Randomization: Randomization assignment will be generated by a computer based randomization table and assigned by a research coordinator not otherwise involved in the study. Assignments will be kept in sealed opaque envelopes numbered sequentially. As an adjunct to standard pre-operative counseling, the physician will call the research coordinator and the next envelope in the sequence will be opened randomizing the patient to the patient-centered or physician centered video

Once randomized, patients will view the video they are assigned to in the waiting room utilizing video viewing devices with headphones. Once the video is complete, patients will receive standard pre-operative counseling for the midurethral sling procedure by their provider. The pre-operative counseling will be scripted. They will then complete the PPQ, preparedness scale, SDS-PFD, DCS.

At the 6 week post-operative visit, they will fill out the questionnaires: SDS-PFD, DRS-PFD, and STAI: Y6, UDI-6, PGI-I will be completed (Table 1). The physician will also complete an adverse events form at that time.

	Baseline Clinic Visit	Immediately after consents and video	6 weeks postoperatively
PPQ		Χ	X
Preparedness Scale		X	
DCS		X	
DRS-PFD			X
SDS-PFD		X	X
UDI-6	X		X
Demographics	X		

Table 1: Outcomes collected at various time points

The primary outcome is preparedness for surgery with an adjunct patient-centered versus a physician-centered video at their pre-operative visit. After they watch the video in the waiting room, all patients will receive standard pre-operative counseling for the midurethral sling procedure by their provider. They will then fill out the preparedness questionnaires. Our secondary outcome is satisfaction, which will also be evaluated using the SDS-PFD at her pre-operative visit after consents and the video as well as their 6 week visit.

The midurethral sling will be performed by surgeons in the standard fashion.

Outcome Measures:

- 1. Patient Preparedness Questionnaire (PPQ): Assess the level of pre-operative preparedness according to each preparedness question. Measured by question 11 on the Patient Preparedness Questionnaire (PPQ): "Overall, I feel prepared for my upcoming surgery." The 11-question PPQ contains questions on both knowledge and preparedness for the planned surgical procedure. The PPQ has demonstrated construct validity properties in previous studies.

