adequate to detect a difference of 40% (Physician-centered video) versus 78% (Patient-centered video) in those being "completely prepared" with 80% power and an alpha of 0.05. This is a feasible power analysis since Firoozi et al found an improvement to 79% using the shared appointments. Therefore our recruitment goal will be to increase randomization to a total of 60 subjects, 30 patients per group, which will also allow for a 20% loss to follow up.

13. Provisions to Monitor the Data to Ensure the Safety of Subjects

There is no DSMB or individual that will be monitoring safety as these procedures, MUS is a common surgical procedures included in the standard of care for stress urinary incontinence. Additionally, there will be a form to report all adverse events throughout the study so this can be reported on.

We do not anticipate any conditions that would trigger a suspension or termination of the research.

14. Withdrawal of Subjects

Any participant may withdraw from the study at any time without penalty and will continue to receive the clinical standard of care. A subject may be withdrawn from the study without her consent at the discretion of the physician and study staff if they believe she no longer meets study inclusion criteria or if she meets exclusion criteria, or if they believe that it is not in her best interest to continue study participation. Investigators may withdraw a subject if the subject is not following the study protocol. If a woman is withdrawn from the study either at her own discretion or that of the research staff, she may continue with the planned surgical procedure performed in the usual fashion.

To minimize withdrawal from the study, patients will be randomized just before the procedure. According to the 2010 CONSORT guidelines, we will analyze all participants assessed for eligibility within the study. We will document reasons for withdrawal from the study including failure to meet eligibility criteria or participant declining enrollment into the study. We will report eligibility criteria not met or reasons for declining participation in the study. The withdrawal procedure is clearly documented in the study consent.

15. Data Management/Confidentiality

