As stated above, the data collection, HIPAA and consent forms will be maintained in a locked file cabinet in the OBGYN administrative area. A separate folder will be designated for each participant. A key matching study number to subject's name will be secured in a locked file cabinet in the OBGYN research administrative area. In order to further ensure patient confidentiality, the identifying information will be kept separately from the numbered study files in a locked cabinet. The data will be maintained for 5 years after completion of the study and then destroyed.

No specimens will be collected. .

17. Risks to Subjects

Risks of enrollment in the study include the risk of breach of confidentiality. We will take every measure to try to ensure the security and confidentiality of participants. This may

Page 14 of 23

result in stigmatization or hardship. Participants will be recruited in a private room and will have ample time to consider whether they want to participate in the study. Also, locked filing cabinets will be used to protect patient consent information and collected data. The link identifying patients and their study numbers will be also stored in a locked cabinet. There are risks of stress, emotional distress, and inconvenience. There are unknown risks of being randomized to either a physician-centered video or a patient-centered video.

Additionally, each patient who will be offered enrollment will already have agreed to a MUS surgery. There are risks inherent to these surgical procedures including bleeding, risk of infection, injury to surrounding organs, especially bladder perforation. We attempt to minimize the possibility of unrecognized injuries by performing cystoscopy with all of these procedures to ensure bladder integrity and to note efflux from each ureteral orifice. Each patient will be provided with informed consent regarding these risks and offered a blood transfusion in the event of life-threatening blood loss. Giving informed consent for these procedures is our practice's standard of care and will not be altered in the study population. The patient and physician-centered videos are an adjunct to routine pre-operative visits.

Pregnant women will not be included in the study, so there is no risk to embryos/fetuses. All women who are of reproductive age routinely get a pregnancy test the day of surgery. If they are pregnant, the patient meets exclusion criteria.

There are no risks to those who are not subjects.

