18. Potential Benefits to Subjects

The patients enrolled are already opting for surgical correction of their stress urinary incontinence. Participation in this study may help to improve an individual participant's condition, but it is also possible that the condition may not improve. There is no guarantee that any individual will personally benefit by participating in this research study. Participation in this study may provide information that may help other people who have a similar medical problem in the future. It is unknown as to whether watching the physician-centered or patient-centered videos will increase satisfaction, preparedness, knowledge, knowledge-recall, and decrease anxiety.

19. Recruitment Methods

.

The urogynecology clinic at UNMH, Westside, SRMC have a large referral population of patients with pelvic organ prolapse. Participants will be identified in the clinics at investigators. The patients will be counseled about possible treatment options for stress urinary incontinence including non-surgical and surgical techniques. If the patients surgical management by a midurethral sling procedure, they will be introduced to the study and provided with written information that may help them decide if participation in the study is right for them. Subjects are encouraged to consult with family, friends,

and primary health care providers, as well as communicate any questions they may have before beginning the written consent process.

If a woman is withdrawn from the study either by her desire or that of the research staff, or does not desire to participate, she will be offered the same treatment options, but she will not watch the videos during her pre-operative visit. Her follow up times for after surgery are the same regardless of participation in the study.

There will be no other additional materials to recruit subjects.

20. Provisions to Protect the Privacy Interests of Subjects

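### Does Section 14's sentence on who is analysed leave the primary comparison without a usable analysis set?

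*Combined protocol and SAP*

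**What the plan says.** Section 14 (Withdrawal of Subjects) cites the 2010 CONSORT guidelines and states that "we will analyze all participants assessed for eligibility within the study". The next two sentences concern recording and reporting why women were ineligible, declined or withdrew. The same section permits withdrawal by staff: "A subject may be withdrawn from the study without her consent at the discretion of the physician and study staff", among other grounds "if they believe she no longer meets study inclusion criteria or if she meets exclusion criteria". It also permits withdrawal for not following the protocol, and it refers to the study consent for the withdrawal procedure.

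Section 17 adds a route that opens after randomisation: "All women who are of reproductive age routinely get a pregnancy test the day of surgery", and "If they are pregnant, the patient meets exclusion criteria". Section 19 says of a woman who withdraws, is withdrawn or declines that she is offered the same treatment options, "but she will not watch the videos during her pre-operative visit".

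Section 11 places check-in, randomisation, video, scripted counselling and questionnaires in one pre-operative visit: "They will then complete the PPQ, preparedness scale, SDS-PFD, DCS". Section 12 names the main comparison (the overall PPQ item, chi-squared test) and defines the two groups by the video to which women were randomised. Sections 5 and 12 set the target at "30 patients per group, which will also allow for a 20% loss to follow up".

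**The concern.** The only sentence that says who is analysed names the wrong population if taken at its word. If it is set aside as flow-diagram language, the published text has no explicit statement that every randomised woman is analysed in her assigned arm, and no rule for a missing item 11.

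That matters more than usual here for three reasons. Patients know their arm, and no passage says that staff are blinded. Staff may withdraw women at their discretion. A pregnancy found on the day of surgery could remove a woman whose primary answer has already been given. The sample size also provides for losing a fifth of each arm, although the primary answer is collected within the randomisation visit, so it is natural to ask which losses the planners had in mind.

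If the choice of whom to count were left until the data had been seen, a few selective exclusions in a 60-woman trial could bias the comparison, and discarding answers already collected would waste power. Section 14 also speaks of randomisation shortly before the procedure, which does not match the rest of the document.

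**Working it through.** **Inputs.** From Sections 5 and 12: 40% versus 78% completely prepared, 80% power, alpha 0.05, 24 evaluable per arm, 30 randomised per arm, 20% loss. Sidedness is not stated; two-sided is assumed.

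**The plan's own figures.**
- Pooled formula: n = [1.960·√(2·0.59·0.41) + 0.842·√(0.40·0.60 + 0.78·0.22)]² / 0.38² = (1.363 + 0.540)² / 0.1444 ≈ 25.1, so 26 per arm. This is within two of the stated 24.
- Exact power is the sum over all (i, j) of Bin(i; n, 0.40)·Bin(j; n, 0.78), counting tables where the uncorrected chi-squared gives p < 0.05. At n = 24 it is 80.1%, which matches the plan.
- Loss: 0.20 × 30 = 6, leaving 24; equally 24 / 0.80 = 30.

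**Power under different amounts of missing data** (same exact method).

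| Case | Rates compared | n per arm | Power |
|---|---|---|---|
| Nothing missing | 40% v 78% | 30 | 86.8% |
| 1 missing per arm, complete cases | 40% v 78% | 29 | 85.0% |
| 1 in 30 missing, counted as not prepared | 38.7% v 75.4% | 30 | 84.0% |
| 6 missing per arm, complete cases | 40% v 78% | 24 | 80.1% |
| 6 in 30 missing, counted as not prepared | 32% v 62.4% | 30 | 67.4% |

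The scaled rates are 0.40 × 29/30 and 0.78 × 29/30 in the third row, and 0.40 × 0.80 and 0.78 × 0.80 in the last. Only the last row falls below 80%, and it needs a fifth of women to leave a same-visit questionnaire blank.

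**One-sided loss, no true effect, 30 per arm.** Remove k unprepared women from one arm only and compute the exact type I error.

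| Prepared in both arms | k = 0 | k = 1 | k = 2 | k = 3 |
|---|---|---|---|---|
| 40% | 4.9% | 5.7% | 5.9% | 7.4% |
| 60% | 4.9% | 6.2% | 7.4% | 9.8% |

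The number of losses, their direction and the 60% rate are assumptions; the documents give none of them.

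**Sensitivity of one result to the missing-data rule.** Assume 10/24 versus 19/24 observed (close to the design rates) and 6 missing per arm.
- Complete cases: p = 0.008.
- All missing counted as not prepared (10/30 v 19/30): p = 0.020.
- All missing counted as prepared (16/30 v 25/30): p = 0.012.
- Every missing woman prepared in the physician arm and unprepared in the patient arm (16/30 v 19/30): p = 0.43.

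The first three rules agree. Only the extreme opposite assignment overturns the result, and it again starts from six missing per arm.

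**The passages side by side.**
- The Section 14 sentence follows the CONSORT reference and precedes text on ineligibility and refusal. A woman with no arm cannot enter a comparison of two arms, so the literal reading cannot alter a result.
- Section 12 groups women by randomised video, which is the ordinary as-assigned comparison.
- The 20% is described as loss to follow-up. Follow-up in this trial is the 6-week visit, where the satisfaction, regret, anxiety and symptom scales are collected and where Table 1 marks the PPQ again. Applying it to the sample size for a pre-operative endpoint is conservative for that endpoint.
- Sections 3, 11 and 15 all put randomisation at the pre-operative visit. The Section 14 phrase is the odd one out, and the procedures in Section 11 are unambiguous.

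**The case for a change.** The strongest argument for a change is that a rule written beforehand costs a few sentences, and its absence leaves a choice open in an unblinded trial where staff may withdraw women. Withdrawal for not following the protocol, if it also removed the data, would amount to a per-protocol exclusion. The pregnancy test falls after the primary answer is given. Calling the Section 14 sentence a slip does not supply the missing statement.

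Part of this stands: no published passage commits to analysing all randomised women or says how an unanswered item 11 is treated. The rest is weaker. Permission to withdraw a woman from the study is not an instruction to delete what she has already answered. The consent form, to which Section 14 refers for the withdrawal procedure, is outside the reviewed text and may settle retention of data, so its silence cannot be assumed. The Section 19 sentence sits under recruitment and also covers women who decline; that any of them would already be randomised is supposition. No frequency is given for pregnancy or for any other withdrawal, and Section 14 says that randomisation was timed to keep withdrawals few.

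**Conclusion.** No change to the plan is needed. The odd phrase in Section 14 is flow-reporting language that cannot be applied to the primary test. The unwritten convention is one that an analyst would fill in the usual way: women in their assigned arm, every available pre-operative item 11 answer used, missing answers reported by arm. The randomisation-timing phrase is a clerical inconsistency.

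With zero or one answer missing per arm, exact power is 84.0% to 86.8% against a planned 80%, whichever simple rule is used. At the protocol's own 40% rate, losing one unprepared woman from a single arm moves type I error from 4.9% to 5.7%. The larger figures (67.4% power, 9.8% type I error, p = 0.43) rest on loss patterns that the documents do not suggest.

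This conclusion assumes a two-sided uncorrected chi-squared test, completion of the PPQ within the randomisation visit as Section 11 describes, and retention of answers already given by women who later withdraw. The last point could not be checked without the consent form.
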